## **7.2. Laboratory Evaluations**

Laboratory data collected during the study, scheduled and unscheduled, will be analyzed and summarized using both quantitative and qualitative methods. The analysis will be based on values reported in conventional units. When values are below the LOQ, they will be listed as such, and the closest imputed value will be used for the purpose of calculating summary statistics as specified in Section 3.7. Hemolyzed test results will not be included in the analysis, but they will be listed in by-subject laboratory listings.

A by-subject listing for laboratory test results will be provided by subject ID number and time point in chronological order for hematology, serum chemistry, and urinalysis separately. Values falling outside of the relevant reference range and/or having a severity grade of 1 or higher on the CTCAE severity grade will be flagged in the data listings, as appropriate.

### **7.2.1. Summaries of Laboratory Results**

A baseline laboratory value will be defined as the last measurement obtained on or prior to the date/time of first dose of andecaliximab/placebo. In the case of multiple values in an analysis window, data will be selected for analysis as described in Section 3.8.3.

Descriptive statistics (n, mean, StD, median, Q1, Q3, minimum, and maximum) will be provided by treatment arm for selected lab test parameters ([Appendix 1](#)) as follows:

- Baseline values
- Values at each post-baseline time point
- Change from baseline at each post-baseline time point

Change from baseline to a post baseline visit will be defined as the visit value minus the baseline value. The mean, median, Q1, Q3, minimum, and maximum will be displayed to the reported number of digits; StD to the reported number of digits plus 1. The mean (+/- SE) of change and percent change from baseline over time will also be plotted for each treatment arm.

Categorical laboratory data will be summarized using the number and percentage of subjects with the given response at baseline and each scheduled post-baseline time point by treatment arm.

### **7.2.2. Graded Laboratory Values**

CTCAE Version 4.03 will be used for assigning toxicity grades (0 to 4) to laboratory results for analysis. Grade 0 includes all values that do not meet the criteria for an abnormality of at least Grade 1. Some laboratory tests have criteria for both increased and decreased levels; analyses for each direction (ie, increased, decreased) will be presented separately.

#### **7.2.2.1. Treatment-Emergent Laboratory Abnormalities**

Treatment-emergent laboratory abnormalities are defined as values that increase at least 1 toxicity grade from baseline at any post-baseline time point, up to 30 days after the last dose of all study treatment, or 55 days after the last dose of andecaliximab /placebo for subjects who permanently discontinued all study treatments, or all available data in the database snapshot for subjects who were still on treatment at the time of analysis. If the relevant baseline laboratory value is missing, then any abnormality of at least Grade 1 observed within the time frame specified above will be considered treatment emergent.

#### **7.2.2.2. Summaries of Laboratory Abnormalities**

The summaries (number and percentage of subjects) for treatment-emergent laboratory abnormalities will be provided by lab test for each treatment arm; subjects will be summarized by the most severe post-baseline abnormality grade for given lab tests.

A by-subject listing of treatment-emergent Grade 3 or higher laboratory abnormalities will be provided by subject ID number and time point in chronological order. This listing will include all test results that were collected throughout the study for the lab test of interest, with all applicable severity grades displayed.

### **7.2.3. Shifts Relative to the Baseline Value**

Shift tables will be presented by showing change in CTCAE grade from baseline to select time points and to the worst post-baseline grade.

### **7.3. Vital Signs and Weights**

Descriptive statistics will be provided by treatment arm for vital signs (temperature, pulse, systolic blood pressure, diastolic blood pressure, and respiratory rate) and weights as follows:

- Baseline value
- Values at each post-baseline visit (including unscheduled and scheduled)
- Change from baseline at each post-baseline visit (including unscheduled and scheduled)

A baseline value will be defined as the last available value collected on or prior to the date/time of first dose of study drug. Change from baseline to a post-baseline visit will be defined as the post-baseline value minus the baseline value.

In the case of multiple values in an analysis window, data will be selected for analysis as described in Section 3.8.3. No formal statistical testing is planned.

A by-subject listing of vital signs will be provided by subject ID number in ascending order and by visit in chronological order. In the same manner, a by-subject listing of body weight will be provided separately.

### **7.4. Prior and Concomitant Medications**

#### **7.4.1. Prior Medications**

Prior medications are defined as any medications begun before a subject took the first study drug.

Prior medications will be summarized by Anatomical Therapeutic Chemical (ATC) drug class Level 2 and preferred name using the number and percentage of subjects for each treatment group and overall. A subject reporting the same medication more than once will be counted only once when calculating the number and percentage of subjects who received that medication. The summary will be ordered alphabetically by ATC medical class and then by preferred term in order of descending overall frequency within each ATC medical class. For drugs with the same frequency, sorting will be done alphabetically.

For the purposes of analysis, any medication with a start date prior to the first dosing date of study drug will be included in the prior medication summary regardless of when the stop date is. If a partial start date is entered the medication will be considered prior unless the month and year (if day is missing) or year (if day and month are missing) of the start date are after the first dosing date. Medications with a completely missing start date will be included in the prior medication summary, unless otherwise specified.

All prior and concomitant medications (other than per-protocol study drugs) will be provided in a by-subject listing sorted by subject ID number and administration date in chronological order.

#### **7.4.2. Concomitant Medications**

Concomitant medications are defined as medications taken while a subject took study drug. Concomitant medications will be summarized by ATC drug class Level 2 and preferred name using the number and percentage of subjects for each treatment group. A subject reporting the same medication more than once will be counted only once when calculating the number and percentage of subjects who received that medication. The summary will be ordered alphabetically by ATC medical class and then by preferred term in descending overall frequency within each ATC medical class. For drugs with the same frequency, sorting will be done alphabetically.

For the purposes of analysis, any medications started prior to or on the first dosing date of study drug and continued to take after the first dosing date, or started after the first dosing date but no later than last dosing date of study drug will be considered concomitant medications. Therefore, medications with a stop date that is on or prior to the date of first dosing date of study drug or a start date that is after the last dosing date of study drug will be excluded from the concomitant medication summary. If a partial stop date is entered, any medication with the month and year (if day is missing) or year (if day and month are missing) prior to the date of first study drug administration will be excluded from the concomitant medication summary. If a partial start date is entered, any medication with the month and year (if day is missing) or year (if day and month are missing) after the study drug stop date will be excluded from the concomitant medication summary. Medications with completely missing start and stop dates will be included in the concomitant medication summary.

Summaries will be based on the Safety Analysis Set. No formal statistical testing is planned.

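### A drug started and stopped on the first dosing date enters neither the prior nor the concomitant medication summary (SAP 7.4.1 and 7.4.2)

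*SAP*

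**What the plan says.** SAP 7.4.1 gives a definition and a working rule for prior medications. The definition is "Prior medications are defined as any medications begun before a subject took the first study drug". The working rule is that "any medication with a start date prior to the first dosing date of study drug will be included in the prior medication summary", whatever the stop date.

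SAP 7.4.2 does the same for concomitant medications. The definition is "Concomitant medications are defined as medications taken while a subject took study drug". The working rule has two inclusion conditions:
- "any medications started prior to or on the first dosing date of study drug and continued to take after the first dosing date"
- "started after the first dosing date but no later than last dosing date of study drug will be considered concomitant medications"

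The section then restates the rule as exclusions. One of them removes "medications with a stop date that is on or prior to the date of first dosing date of study drug"; the other removes drugs begun after the last dosing date.

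For listings, 7.4.1 says: "All prior and concomitant medications (other than per-protocol study drugs) will be provided in a by-subject listing". The introduction to SAP Section 7 separately says that concomitant medication intake will be coded and shown in data listings.

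**The concern.** The two summaries should between them account for every medication recorded up to the last dose. The definitions suggest that they do: a drug begun on Day 1 before the infusion fits the definition of prior, and one given during the infusion fits the definition of concomitant. The working rules use dates only. One asks for a start strictly before the first dosing date and the other asks for use strictly after it, so a record that lies wholly on that date meets neither.

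That date has some interest for safety. The study drug is a humanized monoclonal antibody given by infusion, and a drug used once to treat a reaction to the first infusion would have exactly these dates. Protocol 6.2.3 has sites record all medications at each visit, so the data will exist. SAP 7.1.5.1 counts adverse events with onset on the start date of andecaliximab/placebo as treatment-emergent. A Day 1 reaction is therefore tabulated, while a drug given only that day to treat it is in neither medication table.

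**Working it through.** The plan gives no figure to reproduce; the check is one of logic. Let F be the first and L the last dosing date of study drug, s the medication start date and e its stop date (e ≥ s), all complete.

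Rules as written:
- Prior (7.4.1): s < F.
- Concomitant, inclusion (7.4.2): (s ≤ F and e > F) or (F < s ≤ L).
- Concomitant, exclusion (7.4.2): e ≤ F or s > L.

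**Which records with s ≤ L are in neither table?**
1. Not prior means s ≥ F.
2. If F < s ≤ L, the second inclusion condition applies and the record is concomitant. So s = F.
3. With s = F, the record is concomitant only if e > F. Since e ≥ s = F, the only case left is e = F.

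The single uncovered pattern is s = e = F. An enumeration of all complete date pairs from F − 5 to L + 7, with L = F + 140 as an arbitrary illustration, gave the same answer. It also showed that the inclusion and exclusion sentences of 7.4.2 never disagree with each other. The gap is therefore what the rule says, not the result of two conflicting sentences.

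| Start | Stop | Prior | Concomitant as written | Concomitant after the fix |
|---|---|---|---|---|
| F − 3 | F − 1 | yes | no | no |
| F − 1 | F | yes | no | yes |
| F | F | no | **no** | yes |
| F | F + 1 | no | yes | yes |
| F + 1 | F + 1 | no | yes | yes |

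A one-day drug is counted on Day 2 but not on Day 1.

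**After the fix** (concomitant unless e < F or s > L), the pair (F, F) is concomitant, and no record with a start date from F to L is outside both tables.

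**Conditions for the gap**
- Both dates must be complete. Under 7.4.1 a start date with the day missing, in the month of first dosing, is treated as prior. Under 7.4.2 a stop date with the day missing is excluded only if its month and year come before first dosing.
- The subject must have no other qualifying record of the same drug. Each subject is counted once per medication, so a later record up to the last dosing date brings the subject into the table.
- For a subject who receives a single dose, L = F. The second inclusion condition is then empty, and no medication begun after Day 1 can bring the subject in.

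**The case against.** The strongest reply is that little of consequence is missing. A reader might infer that a safety signal from the first infusion disappears. The documents do not support that. The reaction is a treatment-emergent event under SAP 7.1.5.1. SAP 7.1.6.1 tabulates such events by treatment group, with separate summaries for events related to andecaliximab/placebo and for events leading to its interruption or discontinuation. A subject who stops because of a first-infusion reaction appears there. For a serious event, Protocol 7.3.2.1 also requires the drugs used to be entered in the SAE form. This stands: what is missing is a count of drug use, not the event.

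The record should also be visible in the listings. Read strictly, the 7.4.1 listing covers prior and concomitant medications, and this record meets neither working rule. The wording in Section 7 carries no such date condition, so it would be reasonable to expect the record to be listed.

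Two further readings go too far:
- A drug used from ten days before first dose until Day 1 might be called omitted. It is not; it is in the prior summary. Leaving it out of the concomitant summary is a boundary convention.
- The more lenient handling of an incomplete stop date might be called inconsistent. Keeping a drug whose stop day is unknown is an ordinary inclusive rule, because use may have continued past Day 1.

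It is also fair to say that the rule is the same in both arms and that 7.4.2 plans no formal testing. None of this closes the gap for start = stop = first dosing date, or reconciles it with the section's own definition.

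**Conclusion.** The point holds in a narrow form and is minor. For complete dates, exactly one pattern among medications begun no later than the last dose is left out of both summaries, contrary to the definition of concomitant use in 7.4.2. The medication tables would be incomplete for one-day use on Day 1 where no other record of that drug qualifies. An arm difference confined to such use would not show in them.

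The number of subjects affected cannot be determined. The documents give no rate of Day 1-only treatment, and it could be zero. For scale only, an assumed 1% to 5% of a planned group of 215 would be about 2 to 11 subjects (0.01 × 215 = 2.15; 0.05 × 215 = 10.75). Neither limit comes from the documents.

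The conclusion rests on the date rules being programmed as written. No efficacy result, error rate, exposure summary or adverse event table changes.

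**What to change.** Two sentences in SAP 7.4.2 need to change together; changing only the exclusion would leave it at odds with the inclusion.

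1. Exclusion: leave out a medication only if its stop date is before the first dosing date. Keep the exclusion for drugs begun after the last dosing date.
2. First inclusion condition: started on or before the first dosing date, with a stop date on or after that date, or ongoing. The second condition stays as it is.

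The rule for incomplete stop dates already excludes only earlier months or years, so it needs no change. Section 7.4.1 can also stay as written.

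The cost is a short text edit and one programming condition. The downside is small: a drug stopped earlier on Day 1, before the infusion, will be counted as concomitant, because the rule works on dates and not times. If that drug was begun before Day 1, it will appear in both summaries.

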#### **7.5. Electrocardiogram (ECG) Results**

Electrocardiogram (ECG) analysis results are intended to identify meaningful changes in the QT interval. If potential abnormalities of interest are identified, further analyses may be conducted. Summaries of investigator assessment of ECG readings will be provided for the Safety Analysis Set for each scheduled and unscheduled time point. No formal statistical testing is planned.

##### **7.5.1. Investigator Electrocardiogram Assessment**

A shift table of the investigators' assessment of ECG results at each visit compared with baseline values will be presented by treatment arm using the following categories: normal; abnormal, not clinically significant; abnormal, clinically significant; or missing. The number and percentage of subjects in each cross-classification group of the shift table will be presented. Subjects with a missing value at baseline or post-baseline will not be included in the denominator for percentage calculation. No formal statistical testing is planned.

A by-subject listing for ECG assessment results will be provided by subject ID number and time point in chronological order.

### 7.5.2. Corrected QT Intervals

The QT interval (measured in millisecond [msec]) is a measure of the time between the start of the Q wave and the end of the T wave in the heart's electrical cycle. The QT interval represents electrical depolarization and repolarization of the ventricles. The QT interval is affected by heart rate and a number of methods have been proposed to correct QT for heart rate.

Corrected QT (QTc) intervals will be derived using Fridericia's correction (QTcF) as follows:

$$QTcF = \frac{QT}{\sqrt[3]{RR}}$$

where QT is measured in msec; RR = 60/Heart Rate (beats per min [bpm]) and is measured in seconds

The maximum postdose QTcF interval values obtained during the study will be summarized within the following categories:

- > 450 msec
- > 480 msec
- > 500 msec

The maximum postdose change in QTcF interval values obtained during the study will also be summarized within the following categories:

- > 30 msec
- > 60 msec

QTcF and uncorrected QT values at each visit and change from baseline at each visit will be summarized by treatment arm using descriptive statistics.

### 7.5.3. PR and QRS Intervals

The PR interval (measured in msec) is a measure of the time between the start of the P wave (the onset of atrial depolarization) and the beginning of the QRS complex (the onset of ventricular depolarization). The QRS interval measures the duration of the QRS complex. The maximum ventricular rate (VR) and PR and QRS intervals observed during the study will be categorized. The number and percentage of subjects having values in the following ranges will be presented by treatment arm:

- VR > 100 bpm
- PR interval > 200 msec
- QRS interval > 110 msec

In addition, VR, PR interval, RR, and QRS interval values at each visit and change from baseline at each visit will be summarized by treatment arm using descriptive statistics.

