- 12) Known or suspected central nervous system metastases
- 13) Known dihydropyrimidine dehydrogenase-deficiency (special screening not required)
- 14) Known alcohol or drug abuse or any other medical or psychiatric condition which contraindicates participation in the study
- 15) Documented myocardial infarction or unstable/uncontrolled cardiac disease (ie, unstable angina, congestive heart failure [New York Heart Association  $>$  Class II]) within 6 months of randomization
- 16) Active tuberculosis or history of latent tuberculosis that has not been treated
- 17) Any chronic medical condition that, in the opinion of the Investigator, would make the subject unsuitable for the study or would prevent compliance with the study protocol.
- 18) Serious systemic fungal, bacterial, viral, or other infection that is not controlled or requires intravenous antibiotics
- 19) Experimental medical treatment within 28 days prior to randomization
- 20) Known hypersensitivity to any of the study drugs or excipients or to Chinese hamster ovary cell products or to recombinant human or humanized antibodies, or known allergic reactions to products that contain platinum

- 21) History of long QT syndrome or whose corrected QT interval (QTc) measured using Fridericia's formula ( $QTcF = QT/RR^{0.333}$ ) at screening is prolonged (> 450 ms for males and > 470 ms for females)
- 22) Subjects with potassium, magnesium or calcium less than the lower limit of normal (LLN); electrolyte replacement is permitted during screening

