### **6.2.6. Electrocardiogram Assessment**

A single 12-lead electrocardiogram (ECG) will be collected at Screening, Day 1 of each cycle, at the EOT and EOS visits, per standard practice. Additional ECGs following administration of oxaliplatin will be collected at visits when oxaliplatin is administered after the infusion is completed (i.e., Days 1 and 15 of each cycle, up to a maximum of six 28-day cycles) as required per country label guidance regarding cardiac monitoring. The investigator will review all ECGs and retain the tracing with the source documents. ECGs obtained after oxaliplatin infusions must be reviewed by the investigator/sub investigator before subjects leave the clinic/infusion center.

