### 3.8. Analysis Visit Windows

#### 3.8.1. Definition of Baseline and Study Day

Baseline for efficacy is defined as the last observation within 42 days on or prior to randomization, unless otherwise specified. In the rare cases where the screening assessments are after the randomization date but prior to the first dose of andecaliximab/placebo, the assessments will be considered as baseline.

Baseline for safety is defined as the last observation within 42 days prior to first dose of andecaliximab/placebo, unless otherwise specified.

Study Day 1 for the efficacy analysis will be defined as the day of randomization.

Study Day 1 for the safety analysis will be defined as the day for the first dose of andecaliximab/placebo.

Other study days will be derived as follows:

- Assessment Date – Study Day 1 + 1 if Assessment Date  $\geq$  Study Day 1
- Assessment Date – Study Day 1 if Assessment Date  $<$  Study Day 1

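### The VR, PR and QRS outlier counts in SAP 7.5.3 do not separate abnormalities present at baseline from new ones, and the section does not settle whether pre-dose ECGs count

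*SAP*

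**What the plan says.** **VR, PR and QRS (SAP 7.5.3).** "The maximum ventricular rate (VR) and PR and QRS intervals observed during the study will be categorized". The cuts are VR above 100 bpm, PR above 200 msec and QRS above 110 msec, shown by arm as numbers and percentages. No denominator is stated and nothing refers to baseline status. The section continues: "In addition, VR, PR interval, RR, and QRS interval values at each visit and change from baseline at each visit will be summarized", by arm, with descriptive statistics.

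**QTcF (SAP 7.5.2).** "The maximum postdose QTcF interval values obtained during the study will be summarized within the following categories": above 450, 480 and 500 msec. A second set is relative to baseline: "The maximum postdose change in QTcF interval values obtained during the study will also be summarized within the following categories", above 30 and 60 msec.

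**Eligibility (exclusion criterion 21).** A subject is excluded if QTcF "at screening is prolonged (> 450 ms for males and > 470 ms for females"). No criterion gives a numeric limit for PR, QRS or heart rate.

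**When ECGs are taken and what baseline is.** Protocol 6.2.6: "A single 12-lead electrocardiogram (ECG) will be collected at Screening, Day 1 of each cycle, at the EOT and EOS visits, per standard practice". SAP 3.8.1: "Baseline for safety is defined as the last observation within 42 days prior to first dose of andecaliximab/placebo, unless otherwise specified".

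**Laboratory data, for comparison (SAP 7.2.2.1).** Treatment-emergent abnormalities are "values that increase at least 1 toxicity grade from baseline at any post-baseline time point". Protocol 8.6.4 says that other safety measures will be summarized along lines similar to those for adverse events and laboratory data.

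**The concern.** Two adjacent sections of one ECG analysis use different wording for the data window. QTcF is limited to postdose values. VR, PR and QRS are not, and no reason is given. Read literally, 7.5.3 lets an abnormality seen only at screening put a subject in the table.

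The more durable point is that 7.5.3 takes no account of baseline status. Someone who enters with a PR of 210 msec and stays there is counted beside someone who goes from 170 to 210 msec. Without limits at entry, such subjects can be randomized. For QTcF, the change categories offer a second, baseline-relative view of individual outliers. VR, PR and QRS have no such view: their only baseline-relative summaries are by-visit descriptive changes, in which a few individual outliers are easily lost.

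At stake is how readable a safety table is. A reader comparing arms on a PR above 200 msec cannot tell how much of each percentage was there before treatment.

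**Working it through.** The documents give no ECG outlier rate, so there is no planned figure to reproduce. The check has three parts.

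**1. Does 7.5.3 include pre-dose ECGs?**
- For inclusion: 7.5.3 omits the word postdose that 7.5.2 uses, a screening ECG exists for every subject, and SAP 7 says that baseline as well as post-baseline safety data are summarized.
- Against: protocol 8.6 restricts safety summaries to data from the first-dose date onward and sends pre-treatment data to listings. SAP 7 also lists pre-treatment data, and SAP Table 3-2 opens the post-baseline ECG window after the first dose.
- Left open: an ECG taken on the first-dose date but before the infusion falls inside the protocol 8.6 window, and under SAP 3.8.1 it may be the baseline itself.

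The window is ambiguous. The answer matters only for a subject over the cut before dosing and never afterwards. A subject over the cut both before and after dosing is counted on either reading.

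**2. Size for VR, PR and QRS (illustration; all rates assumed)**

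Let b be the share over the cut at baseline, s the share of those who stay in the table, and q the new postdose rate among the rest. Then:

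table rate = b·s + (1 − b)·q

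The figures take s = 1, which is exact under the literal reading and an upper case if only postdose values count. Inputs: q = 5% on placebo and 10% on active treatment (true ratio 2.0, difference 5.0 points), and 215 subjects per arm from the sample size section.

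| b | Placebo | Active | Ratio | Difference (points) | Baseline cases per arm (215·b) | Pre-existing share of placebo count |
|---|---|---|---|---|---|---|
| 0% | 5.0% | 10.0% | 2.00 | 5.0 | 0 | 0% |
| 2% | 0.02 + 0.98 × 0.05 = 6.9% | 0.02 + 0.98 × 0.10 = 11.8% | 1.71 | 4.9 | 4.3 | 29% |
| 5% | 0.05 + 0.95 × 0.05 = 9.75% | 0.05 + 0.95 × 0.10 = 14.5% | 1.49 | 4.75 | 10.8 | 51% |
| 10% | 0.10 + 0.90 × 0.05 = 14.5% | 0.10 + 0.90 × 0.10 = 19.0% | 1.31 | 4.5 | 21.5 | 69% |

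The difference shrinks only by the factor (1 − b). With equal new rates in both arms the expected difference stays at 0, so neither arm is favored.

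**3. Size for QTcF**

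Under exclusion criterion 21 no eligible man is above 450 msec at screening, and no eligible subject is above 480 or 500. Carry-over is essentially confined to the row above 450, in women entering at 451 to 470 msec. Small exceptions are eligibility deviations and a pre-dose Day 1 reading higher than the screening one. If women are 25% to 40% of subjects and 2% to 10% of them lie in that band (both assumed):
- Low: 215 × 0.25 × 0.02 = 1.1 subjects per arm (0.5%)
- High: 215 × 0.40 × 0.10 = 8.6 subjects per arm (4.0%)

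**The case against.** The best defense is that these are descriptive counts of absolute maxima in a randomized, double-blind trial. SAP 7.5 plans no formal ECG testing and allows further analysis if something of interest appears. Baseline abnormalities should fall equally on both arms in expectation. Baseline context exists: by-visit changes for all three measures, and a shift table of the investigator's overall ECG reading in 7.5.1. Laboratory values have toxicity grades and these intervals are not graded in the plan, so a different convention is not in itself an error.

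Most of this stands, and it limits the weight of the point. It does not remove it. The shift table is not specific to any interval, by-visit means do not identify individual outliers, and protocol 8.6.4 points toward the adverse event and laboratory approach.

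A reader might also infer more than the documents support:
- *That screening ECGs are certainly in the table.* Protocol 8.6, SAP 7 and Table 3-2 pull the other way, and the window is only unclear.
- *That pre-existing abnormalities are reported as on-treatment findings.* No section gives the 7.5.3 counts that label. They are simply not told apart from new ones.
- *That a cardiac signal would be hidden.* The ratio is diluted, but at an assumed 10% baseline prevalence the difference moves only from 5.0 to 4.5 points.
- *That QTcF has the same problem.* It is already limited to postdose values, has change categories, and is bounded by exclusion criterion 21.
- *That the stated aim in SAP 7.5 covers PR, QRS and VR.* The aim named there is meaningful change in the QT interval.

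**Conclusion.** The point holds as a modest defect of specification. Section 7.5.3 leaves its data window unclear and merges pre-existing with new VR, PR and QRS abnormalities. A persistent baseline abnormality is counted however the window is read.

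The consequence is higher rates in both arms and a ratio pulled toward 1: from 2.0 to between 1.71 and 1.31 for baseline prevalences of 2% to 10%. That range rests on assumed new-onset rates of 5% and 10% and on every subject over the cut at baseline staying in the table. If fewer stay, the dilution is smaller. For QTcF the effect is minor and essentially limited to one row in one sex. No efficacy result or formal test is touched. The change is worth making because it is cheap, not because the current table would mislead badly.

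**What to change.** 1. In SAP 7.5.3, define the categorized value as the maximum postdose VR, PR or QRS, in line with 7.5.2.
2. Present the VR, PR and QRS categories, and the QTcF row above 450 msec, cross-classified by baseline status (at or below the cut, or over it), among subjects with a baseline and at least one postdose ECG.
3. Report the new-onset count and percentage among those at or below the cut at baseline, and keep those already over it in their own row.

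Cross-classifying is better than dropping subjects who start over the cut. A subject going from a PR of 205 to 280 msec would otherwise leave the count altogether. The row keeps such subjects in view, although how far they moved must still be read from the change-from-baseline data.

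The cost is SAP wording and one programming condition on ECGs already collected, a slightly larger table, and a smaller denominator for the new-onset rate.
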